4. Continuous eligibility assessments on Day -1 will be done only during Period 1, and continuous medical history on Day -1 and prior to dosing on Day 1 of each period.
5. Including sex, date of birth, race, and ethnicity.
6. Will be performed at Screening, at the admission of each period (Day -1), for each period: on Day 1 pre-dose (up to 60 minutes pre-dose), and 1 (± 20 min), 2 (± 20 min), 4 (± 20 min), 8 (± 60 min), 12 (± 60 min), and 16 (± 60 min) hours post-dose; on Day 2 (24 [± 60 min] hours post-dose); on Day 3 (48 [± 60 min] hours post-dose), and at Follow-up. Orthostatic vital signs will be measured at Screening and at admission on Day -1 only.
7. Will be started approximately 1-2 hours pre-dose at Day 1 of each period and will be continued to approximately 48 hours post-dose.
8. Will take place at Screening (in fasted state, i.e., participants should fast for 4 hours prior to sample collection), and in each period: on Day -1 (in fasted state), Day 1 at 8 hours post-dose (in not-fasted state), at Day 2 (in fasted state), at Day 3 (in fasted state), and at Follow-up (in fasted state). HbA1c will be performed at Screening.
9. Participants receiving Treatment A will be required to consume a high-calorie, high-fat meal 30 minutes prior to study drug administration. Participants receiving Treatment B will be administered the study drug under fasted state.
10. Will take place at pre-dose (within 2 hours of dosing) and at 0.25 (± 2 min), 0.5 (± 2 min), 1 (± 5 min), 1.5 (± 5 min), 2 (± 5 min), 3 (± 10 min), 4 (± 10 min), 6 (± 10 min), 8 (± 10 min), 12 (± 10 min), 16 (± 30 min), 24 (± 30 min), 36 (± 30 min), 48 (± 30 min), 72 (± 1 hr), and 96 (± 1 hr) hours post-dose.
11. In potential post-menopausal women only to confirm the post-menopausal status.
12. Women of childbearing potential (only) will have a urine pregnancy test at Screening and at discharge on Day 3, and a serum pregnancy test on Day -1 of each period.

Table 3: Schedule of Assessments (Part 2)

	Screening	Treatment						Outpatient Visits		Follow-Up ¹
	D-28 to -2	D-1	D1	D2	D3-11	D12	D13 (Discharge ² or early termination)	D15	D16	D19 (or between Day 19 and Day 22)
Informed consent	X									
Height and BMI	X									
Weight	X	X					X			
Inclusion/Exclusion Criteria	X	X ³	X ³							
Demographics ⁴	X									
Medical History		X ³								
Concomitant Medications							Continuously			
Physical and Neurological Examination	X	X					X			X

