 - on Day 9: pre-dose (within 2 hours of dosing),
 - on Day 10: pre-dose (within 2 hours of dosing),
 - on Day 11: pre-dose (within 2 hours of dosing),
 - on Day 12: pre-dose (within 2 hours of dosing) and 0.25 (± 2 min), 0.5 (± 2 min), 1 (± 5 min), 1.5 (± 5 min), 2 (± 5 min), 3 (± 10 min), 4 (± 10 min), 6 (± 10 min), 8 (± 10 min), 12 (± 10 min), and 16 (± 30 min) hours post-Day 12 dose and
 - on Day 13: at 24 hours (± 30 min) and 36 hours (± 30 min) post-Day 12 dose,
 - on Day 15: at 72 (± 1 hr) hours post-Day 12 dose (outpatient visit), and
 - on Day 16: at 96 (± 1 hr) hours post-Day 12 dose (outpatient visit).
10. In potential post-menopausal women only to confirm the post-menopausal status.
11. Women of childbearing potential (only) will have a urine pregnancy test at Screening and at discharge on Day 13, and a serum pregnancy test on Day -1.

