6 OBJECTIVES AND ENDPOINTS

Objectives	Endpoints
Part 1a	
Primary	
To assess the single dose safety and tolerability of ATH-399A in healthy male and female participants in up to 5 different ascending dose level groups.	Safety and tolerability will be assessed by changes in vital signs, ECGs, clinical laboratory tests, telemetry, physical examination, neurological examination, C-SSRS, and the overall incidence of AEs and SAEs.
Secondary	
To evaluate the single dose plasma pharmacokinetics (PK) of ATH-399A in healthy male and female participants in up to 5 different ascending dose level groups.	Plasma PK parameters will include: 
• AUC_{0-t}• $AUC_{0-\infty}$• C_{max}• T_{max}• λ_z• $t_{1/2 el}$
To determine concentration of ATH-399A and identify its metabolites in blood and urine in healthy male and female participants after a single dose in up to 5 different ascending dose level groups.	Concentrations of ATH-399A and identification its major metabolites in blood and urine.
Part 1b	
Primary	
To assess the single dose safety and tolerability of ATH-399A in healthy male and female participants under fasted and fed conditions.	Safety and tolerability will be assessed by changes in vital signs, ECGs, clinical laboratory tests, telemetry, physical examination, neurological examination, C-SSRS, and the overall incidence of AEs and SAEs.
Secondary	
To evaluate the single dose plasma PK of ATH-399A in healthy male and female participants under fasted and fed conditions.	Plasma PK parameters will include: 
• AUC_{0-t}• $AUC_{0-\infty}$• C_{max}• T_{max}• λ_z• $t_{1/2 el}$

Objectives	Endpoints
Part 2	
Primary	
To assess the safety and tolerability of multiple doses of ATH-399A in up to 2 ascending dose groups in healthy male and female participants.	Safety and tolerability will be assessed by changes in vital signs, ECGs, clinical laboratory tests, telemetry, physical examination, neurological examination, C-SSRS, and the overall incidence of AEs and SAEs.
Secondary	
To assess the plasma PK of multiple doses of ATH-399A in up to 2 ascending dose groups in healthy male and female participants.	
Plasma PK parameters will include:
 
• AUC_{0-t}• $AUC_{0-\infty}$• C_{max}• $C_{max, ss}$• C_{min}• C_{avg}• T_{max}• $T_{max, ss}$• $AUC_{0-\tau}$ (AUC_{0-24}, Day 12 dose)• AUC_{0-24} (Day 1 dose)• λ_z• $t_{1/2 el}$• AR

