11.6.1 Physical and Neurological Examinations

A complete physical examination will be performed at screening, at the admission and at the discharge and will include assessments of the following: head, eyes, ears, nose, throat (HEENT), neck, chest, lungs, abdomen, musculoskeletal, dermatological, cardiovascular/peripheral vascular, and general neurological examination.

A brief physical examination will be performed at all other times, and will include assessments of the following: HEENT, chest, lungs, abdomen, dermatological, cardiovascular/peripheral vascular, and areas of note elicited from the participant.

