13.2 Appendix 2: Clinical Laboratory Tests

- The tests detailed in [Table 7](#) will be performed by the local laboratory at the time points specified in the SoAs.
- Additional tests may be performed at any time during the study as determined necessary by the Investigator or required by local regulations.

Table 7: Protocol-required Safety Laboratory Tests

Serum or urine pregnancy:	β-human chorionic gonadotropin (β-hCG); urine pregnancy test at screening and follow-up, and serum pregnancy test on Day -1 for WOCBP; in the absence of 12 months of amenorrhea, confirmation with at least one FSH measurement (≥ 40 IU/L or mIU/mL or per local threshold for defining postmenopausal state is required.
Hematology:	Hematocrit, hemoglobin, platelet count, RBC count, RBC distribution width, WBC count and differential: 
• Basophils• Eosinophils• Lymphocytes• Monocytes• Neutrophils
Clinical Chemistry:	Albumin, Alkaline phosphatase, ALT, AST, calcium, chloride, creatinine, creatine kinase, estimated glomerular filtration rate (eGFR, calculated using the MDRD equation), gamma-glutamyl transferase, glucose, phosphorus, potassium, sodium, total, direct and indirect bilirubin, total protein, urea (BUN).
Thyroid Panel:	TSH, FT3, FT4
Coagulation:	Prothrombin time (PT, unless not available due to local laboratory reporting standards), activated partial thromboplastin time (aPTT), and international normalized ratio (INR)
Urinalysis:	macroscopic examination, pH, specific gravity, protein, glucose, ketones, bilirubin, occult blood, nitrite, urobilinogen, and leukocytes. Unless otherwise specified, microscopic examination will be performed on abnormal findings.
Serology:	HIV antigen/antibody, HbsAg, HCV antibody, COVID-19 PCR
Urine Drug Screen:	Amphetamines, methamphetamines, methadone, barbiturates, benzodiazepines, cocaine, opiates, methyl-enedioxy methamphetamine (MDMA), methadone, phencyclidine, and tetrahydrocannabinol
Breath Test:	Alcohol
Other:	HbA1c (Only at screening)

Investigators must document their review of each laboratory safety report.

13.3 Appendix 3: AEs and SAEs: Definitions and Procedures for Recording, Evaluating, Follow-up, and Reporting

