4.3 Part 2 (MAD)

4.3.1 Primary Endpoints

- Changes from baseline in vital signs, ECGs, clinical laboratory tests, telemetry, physical examination, neurological examination, C-SSRS, and the overall incidence of AEs and SAEs.

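### Section 11.6.1 leaves the neurological examination out of the follow-up visit where Tables 1-3 schedule it, and Part 2 alone has no C-SSRS at follow-up

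*Protocol*

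**What the plan says.** **Endpoints.** Protocol Section 6 defines the primary endpoint of every part in the same terms: "Safety and tolerability will be assessed by changes in vital signs, ECGs, clinical laboratory tests, telemetry, physical examination, neurological examination, C-SSRS", together with the incidence of adverse events. SAP Section 4.3.1 repeats this for Part 2 as "Changes from baseline in vital signs, ECGs, clinical laboratory tests, telemetry, physical examination, neurological examination, C-SSRS, and the overall incidence of AEs and SAEs", and SAP Sections 4.1.1 and 4.2.1 do the same for Parts 1a and 1b.

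**Neurological examination.** In Section 4.1, the row "Physical and Neurological Examination" is marked in Tables 1, 2 and 3 at screening, Day -1, discharge and follow-up. Section 11.6.1 sets the content of the examination by visit. "A complete physical examination will be performed at screening, at the admission and at the discharge", and this version includes a general neurological examination. Then: "A brief physical examination will be performed at all other times, and will include assessments of the following: HEENT, chest, lungs, abdomen". The brief list goes on to skin, cardiovascular system and whatever the participant draws attention to, and ends there.

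**C-SSRS.** Tables 1 and 2 mark it at screening, Day -1 and follow-up. Table 3 marks it at screening, Day -1 and Day 13, with no mark at follow-up.

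**Pregnancy test.** Table 7 (Section 13.2) gives "urine pregnancy test at screening and follow-up, and serum pregnancy test on Day -1 for WOCBP". Footnote 11 of Table 3 gives "urine pregnancy test at Screening and at discharge on Day 13". Footnote 11 of Table 1 and footnote 12 of Table 2 likewise name discharge, on Day 3. None of the three schedules marks a pregnancy test at follow-up.

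**The concern.** This is a first-in-human study of a drug aimed at midbrain dopamine neuron biology, and the neurological examination and the C-SSRS are named components of the primary safety endpoint. Synopsis and Section 7.3 text on the SRC asks for safety and tolerability data through the final follow-up visit before escalating and before moving from Part 1a to Parts 1b and 2.

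If sites follow 11.6.1, that data package has no neurological examination from the follow-up visit in any part. A sign without a symptom that appeared or persisted after discharge would not be looked for. In Part 2, which has twelve daily doses and includes the cohort aged over 55 to 80, the package also has no C-SSRS from follow-up, although the single-dose parts collect one there. The protocol gives no reason for the difference.

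The pregnancy-test item is of a different kind. It is a disagreement about when a test is done and does not touch an endpoint.

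**Working it through.** There is no sample-size or power figure to reproduce. The check sets the passages side by side and counts days and participants.

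**1. Scheduled visits, from Tables 1-3 and their footnotes**

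| Assessment | Part 1a (Table 1) | Part 1b (Table 2) | Part 2 (Table 3) |
|---|---|---|---|
| Physical and neurological examination | Screening, D-1, D3, follow-up | Screening, D-1, D3, follow-up | Screening, D-1, D13, follow-up |
| C-SSRS | Screening, D-1, follow-up | Screening, D-1, follow-up | Screening, D-1, D13 |
| Pregnancy test (WOCBP) | Screening, D-1, D3 | Screening, D-1, D3 | Screening, D-1, D13 |

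The empty follow-up cell for the C-SSRS in Table 3 is unlikely to be a conversion fault. The pregnancy row of that table has the same pattern of marks, and its footnote confirms Day 13.

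**2. Neurological examination: schedule against content**

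- The schedules mark four kinds of visit: screening, admission, discharge and follow-up.
- 11.6.1 gives the complete examination to the first three.
- The only scheduled visit left for the brief examination is follow-up, so the brief-examination rule in effect governs that visit alone. It removes the component that the schedule row names.
- Participants affected if 11.6.1 is followed: 40 + 12 + 16 + 8 = 76 planned. Of these, 16 receive placebo: 5 × 2 = 10 in Part 1a and 3 × 2 = 6 in Part 2.

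**3. C-SSRS in Part 2**

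- Last dose Day 12; last C-SSRS Day 13: 13 − 12 = 1 day after the last dose.
- Follow-up Day 19 to 22: 19 − 12 = 7 to 22 − 12 = 10 days after the last dose.
- Interval without a C-SSRS: 19 − 13 = 6 to 22 − 13 = 9 days.
- Participants: 16 + 8 = 24, in three cohorts of 6 active and 2 placebo, so 18 active and 6 placebo.
- For comparison, the Part 1a C-SSRS at follow-up (Day 8 to 11) falls 7 to 10 days after the Day 1 dose.

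**4. Pregnancy test**

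- Part 1a: discharge Day 3 against follow-up Day 8 to 11, a difference of 5 to 8 days.
- Part 2: discharge Day 13 against follow-up Day 19 to 22, a difference of 6 to 9 days.

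**5. Use in the analysis**

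- SAP 10.7 lists physical and neurological results by participant.
- SAP 10.8 lists the C-SSRS and summarises change in responses by treatment. SAP 6.1 presents each part separately.
- SAP 7.8 lists pregnancy tests under Study Population; the laboratory summaries in SAP 10.3 do not include them.
- SAP Section 10 plans no inferential analysis of safety data.

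**The case against.** **The schedules control timing.** Sections 11 and 11.6 refer to the Schedules of Assessments for when assessments are done, and 11.6.5 does the same for laboratory tests. On that basis a site would do the neurological examination at follow-up because three tables say so. One can also argue that the brief-examination rule concerns only the physical examination. This stands in part: the schedules settle when, and a careful site could still do the examination. But 11.6.1 is headed as covering both examinations, is the only section that sets their content, and does so by visit. It gives the follow-up visit no neurological content, so the conflict remains.

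**The Part 2 C-SSRS is a choice, not a contradiction.** This is correct. No passage requires a C-SSRS at follow-up in Part 2. Every part has one after dosing, and a Part 2 change from baseline can be computed from Day 13. Adverse events are collected until follow-up (11.7.1), and 11.6.6 covers anyone judged at risk. What remains is an unexplained inconsistency between parts that is cheap to remove.

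**Stronger readings that the documents do not support:**

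- A reader might infer that there is no neurological examination, or in Part 2 no C-SSRS, after dosing ends. That is not so. The discharge examination includes the neurological component and follows the last dose in every part, and Part 2 has the Day 13 C-SSRS. The gap is after discharge.
- A reader might count the pregnancy test as a primary-endpoint assessment because Table 7 lists it among the clinical laboratory tests. The endpoint text does not name it, and the SAP only lists it.
- A reader might argue that a discharge test comes too early to detect a recent conception, so that Table 7 must be right. The documents contain nothing on assay detection times. The text directly above Table 7 itself defers to the time points in the schedules, so Table 7 cannot be taken as the authority.

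**SRC timing.** Section 13.1.5.1 sets a shorter minimum for SRC safety data (48 hours after the dose in the SAD part, 24 hours after the last dose in the MAD part) than the Synopsis and Section 7.3. The argument about the SRC package rests on the latter two.

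**Conclusion.** The point holds, with three items of unequal weight.

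1. **Neurological examination.** This is a real conflict between Section 11.6.1 and Tables 1-3 over a named primary-endpoint component. If 11.6.1 is followed, about 76 planned participants have no neurological examination after discharge.
2. **C-SSRS in Part 2.** This is an inconsistency between parts without a stated reason. About 24 participants (18 active, 6 placebo) have no C-SSRS in the 6 to 9 days between Day 13 and the follow-up visit.
3. **Pregnancy test.** This is a minor scheduling conflict of 5 to 8 days in Part 1a and 6 to 9 days in Part 2, with no bearing on an endpoint.

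The effect is on the completeness of follow-up safety data and on what the SRC sees; no inferential result changes. The counts assume planned enrolment. The first item also assumes that sites take the content of the follow-up examination from 11.6.1.

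**What to change.** - **Section 11.6.1:** state that the follow-up examination includes the neurological examination that Tables 1-3 already schedule. This is one sentence.
- **Table 3:** add the C-SSRS (Since Last Visit version) at the existing Day 19-22 visit, in line with Tables 1 and 2, and keep Day 13. This is one table cell. The downside is a few minutes per participant at a visit already attended.
- **Section 13.2, Table 7, and the footnotes of Tables 1-3:** reconcile them so that the second urine pregnancy test has one stated time. This review does not say which time it should be.

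The SAP methods need no change. The added Part 2 time point would enter the listing and the change summary already planned in SAP 10.8.

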11.6.2 Vital Signs

The Investigator or qualified designee will assess vital signs as noted in the SoA. Vital signs include temperature, blood pressure, pulse rate, and respiratory rate. The participant will be instructed to rest in the supine position for at least 5 minutes before vital signs are assessed.

11.6.3 Electrocardiograms

12-Lead ECGs will be performed in triplicate, at least 1 minute apart, all within 10 minutes, and will be performed and interpreted according to the site's standard operating procedures. Average

values should be recorded. The ECGs will be performed after the participant has been resting in a supine position for at least 5 minutes. The ECG will electronically measure and calculate ventricular heart rate and the PR, RR, QRS, QT, and QTcF intervals. The QTcF interval will be used for clinical evaluations.

If a clinically significant abnormality is detected, the abnormality should be documented as an AE and followed until resolution with additional ECGs as medically indicated.

11.6.4 12-Lead Telemetry

12-Lead telemetry for evaluation of cardiac arrhythmias will be conducted at the time points noted in the SoAs.

11.6.5 Clinical Safety Laboratory Tests

- See [Section 13.2](#) for the list of clinical laboratory tests to be performed and the SoA ([Section 4.1](#)) for the timing and frequency.
- The Investigator must review the laboratory results, document this review, and record any clinically significant changes occurring during the study as an AE. The laboratory results must be retained with source documents ([Section 10.1](#)).
- All laboratory tests with values considered clinically significantly abnormal during participation in the study should be repeated until the values return to normal or baseline or are no longer considered clinically significant by the Investigator or MM.
 - If clinically significant values do not return to normal/baseline within a period of time judged reasonable by the Investigator, the etiology should be identified, and the Sponsor notified.
 - All protocol-required laboratory tests, as defined in [Section 13.2](#), must be conducted in accordance with the site's standard procedures or SOPs.
 - If laboratory values from non-protocol-specified laboratory tests performed at the institution's local laboratory require a change in participant management or are considered clinically significant by the Investigator (eg, SAE or AE or dose modification), then the results must be recorded.

11.6.6 Columbia-Suicide Severity Rating Scale (C-SSRS)

The C-SSRS is a validated instrument to prospectively assess suicidal ideation and behavior (<http://www.cssrs.columbia.edu>). There are versions of the questionnaire designed for use at screening (Baseline/Screening version) and at baseline and visits throughout the study (Since Last Visit version). All versions of the C-SSRS include a series of screening questions related to suicidal ideation and suicidal behavior. Participant responses of “yes” to one or more screening questions will prompt additional questions that evaluate frequency and intensity of suicidal ideation and/or behavior. Participants with active suicidal behavior or suicidal ideation of type 4 (active suicidal ideation with some intent to act, without specific plan) or type 5 (active suicidal

ideation with specific plan and intent) based on the C-SSRS in the 12 months before screening based on the C-SSRS will not be eligible to participate. If the Investigator determines that a participant is at risk of suicide or self-harm, appropriate measures to ensure the participant's safety and obtain mental health evaluation must be implemented: refer to the family physician and/or to the nearest hospital. A complete evaluation and medical care should be provided rapidly.

The C-SSRS will be administered and scored by the Investigator or qualified clinical unit personnel.

11.7 Adverse Events (AEs), Serious Adverse Events (SAEs), and Other Safety Reporting

The definitions of AEs and SAEs can be found in [Section 13.3](#).

The Investigator and any qualified designees are responsible for detecting, documenting, and recording events that meet the definition of an AE or SAE and remain responsible for following AEs to resolution and/or stabilization. This includes events reported by the participant (or, when appropriate, by a caregiver, surrogate, or the participant's legally authorized representative).

The method of recording, evaluating, and assessing causality of AEs and SAEs and the procedures for completing and transmitting SAE reports are provided in [Section 13.3](#).

11.7.1 Time Period and Frequency for Collecting AE and SAE Information

All AEs will be collected continuously from time of informed consent until the Follow-up Visit ([Section 4.1](#)).

Medical occurrences that begin after obtaining informed consent will be recorded as AEs.

All SAEs will be recorded and reported to the Sponsor or designee immediately and under no circumstance should this exceed 24 hours, as indicated in [Section 13.3](#). The Investigator will submit any updated SAE data to the Sponsor within 24 hours of it being available.

Investigators are not obligated to actively seek information on new AEs or SAEs after conclusion of the study participation. However, if the Investigator learns of any SAE, including a death, at any time after a participant has been discharged from the study, and the Investigator considers the event to be reasonably related to the study treatment or study participation, the Investigator must promptly notify the Sponsor.

11.7.2 Method of Detecting AEs and SAEs

Care will be taken not to introduce bias when detecting AEs and/or SAEs. Open-ended and nonleading verbal questioning of the participant is the preferred method to inquire about AE occurrences.

11.7.3 Follow-up of AEs and SAEs

After the initial AE/SAE report, the Investigator is required to proactively follow each participant at subsequent visits/contacts. All SAEs will be followed until resolution, stabilization, the event is otherwise explained, or the participant is lost to follow-up (as defined in [Section 10.4](#)). Further information on follow-up procedures is provided in [Section 13.3](#).

